12.3 Planned Interim Analyses (if applicable)

If any interim analyses are to be conducted this will take place without unblinding.

12.3.1 Safety Review

Analysis of adverse events will use the safety sample, defined as all randomized participants who received at least one cycle of study medication.

12.3.2 Efficacy Review

The study's primary aim is to evaluate the effects of Erenumab in reducing pain level and secondary outcomes in participants with chronic TMD. The primary endpoint is change from Visit 0 to Visit 4 in average pain level (0-100) calculated in the month prior to the visit. Secondary outcomes are TMD pain days, jaw function, pain-related disability, and other pain related outcomes.

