The study drug is Erenumab 70mg, SC injection. After randomization and on Visit 1, the participant will receive the drug or placebo. This same treatment will be administered once a month for 3 months (3 cycles/12 weeks). The primary end point will be a change in the average pain index score from baseline, representing the mean of daily average pain intensity score values (0-100 scale) derived from Daily Symptom Diaries for 12 weeks (12 weeks treatment).

Secondary end points will be participant ratings of other pain related outcomes, examiner assessment of pain, occurrence of symptoms and adverse events.

Exploratory end points are change of [REDACTED]
[REDACTED] cytokine profiles [REDACTED]

Objectives:	Primary: To investigate the efficacy of Erenumab compared to placebo on the reduction of pain scores in patients with TMD during a 12-week treatment period. Secondary: To determine the efficacy of Erenumab on the proportion of subjects with at least 50% reduction from baseline in mean monthly TMD pain days and to determine the efficacy of Erenumab using functional measures namely, jaw functional limitation, pressure pain thresholds and oral behaviors disability, and emotional functioning. Exploratory: To investigate the efficacy of Erenumab in [REDACTED] cytokine release [REDACTED] [REDACTED]
Population:	60 adults of either sex and any ethnicity between the ages of 18 and 65 years with a diagnosis (According to the Diagnostic Criteria for Temporomandibular Disorders (DC/TMD) for Clinical and Research Applications) of chronic TMD (myalgia +/- arthralgia) and no contraindications for the use of Erenumab will be enrolled from the Brotman Facial Pain Clinic and the Oral and Maxillofacial Surgery clinic from the University of Maryland, School of Dentistry.
Phase:	II
Number of Sites:	University of Maryland, School of Dentistry
Description of Intervention:	Study drug is Erenumab 70mg or an inert placebo will be administered by subcutaneous injection once a month (3 cycles) over a 12-week period.
Study Duration:	36 months

[figure not shown]
Subject 21 weeks

Participation

Duration:

Estimated Time to Complete Approximately 2.5 years (30 months)
Enrollment:

Schematic of Study Design:

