3.2 Study Outcome Measures

3.2.1 Primary

The primary endpoint will be a monthly mean pain intensity score change from baseline, representing the arithmetic mean of daily average pain intensity score values. The daily average pain intensity score will be measured on a 0-100 numeric rating scale (NRS) and reported in the Daily Symptom Diary (DSD). The monthly mean pain intensity score will be determined from baseline, for each month/cycle (4 weeks/28 days) during the 12 weeks (3 cycles) of treatment and the last month prior last visit (Follow up).

The monthly mean pain intensity score will be calculated if a participant has at least 80% compliance with the DSD.

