4 STUDY DESIGN

60 patients (30 per each arm) aged 18-65 years old of either sex, and any race or ethnicity presenting chronic painful temporomandibular disorders (TMD) will be randomly assigned in a 1:1 parallel, double-blind, phase 2 single center clinical trial, to receive either Erenumab or placebo. Participants will attend 6 clinic visits (Visit 0-Visit 5) over a period of 21 weeks. The study should be completed over a period of 3 years, with an estimated duration of recruitment of 2.5 years.

Participants will be pre-screened in person at the Brotman Facial Pain clinic, the Oral and Maxillofacial Surgery Clinic both at the University of Maryland, School of Dentistry or by telephone. Potentially eligible and interested participants will be scheduled for a Screening and Baseline Visit (Visit 0). During Visit 0, participants will provide informed consent and be evaluated for eligibility; information including demographics, medical history, concomitant medications, and therapies will be collected. In addition, participants will be assessed for pain level, pain symptoms, jaw function, health status, among other measures and a blood sample will be collected. Procedures will include clinical examinations and tests and the dispensation of various questionnaires, all of which are listed in the Schedule of Events (Appendix A).

Participants who show compliance with the Daily Symptom Diary of at least 80% and who meet the pain score (inclusion criteria) for 28 days/4 weeks (baseline period) after Visit 0, will be randomly assigned to one of two groups (Erenumab or placebo) and will be scheduled for Visit 1 within a week of randomization.

At Visit 1, randomized participants will receive the 1st cycle of management and begin a 12-week drug treatment/placebo phase that will be divided into once a month injection/cycle for a total of 3 cycles. During that period, Visits 2-4 will take place, and many of the baseline assessments will be repeated. Between visits, communication will be conducted by telephone. The final study visit, visit 5, will occur 4 weeks after the last assessment (visit 4) and 8 weeks after the last dosage of drug treatment (Visit 3).

The primary endpoint will be the change in a monthly mean pain intensity score derived from the Daily Symptom Diary. Efficacy will be evaluated as the difference between Erenumab arm and the placebo arm in the monthly pain intensity score (on a 0-100 scale) during the 12 week treatment period.

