12 STATISTICAL CONSIDERATIONS

12.1 Study Hypotheses

The main objective of the statistical analysis is to estimate change in study endpoints and evaluate the efficacy of Erenumab by testing a priori hypothesis concerning the differences between treatment and placebo.

Erenumab reduces pain and restores function in patients suffering of TMD.

The primary efficacy hypothesis is that Erenumab produces greater change in average pain score (0-100 scale) from Visit 1 to Visit 4 than placebo.

The secondary efficacy hypothesis is that Erenumab produces a greater proportion of patients reaching at least a 50% reduction from baseline in monthly TMD pain days compared to placebo. This will be determined as a change from baseline phase (4 weeks) through the 12 weeks treatment phase (3 cycles) until Visit 4.

Functional measures related to TMJ biomechanics and pain related behaviors:

There is a greater proportion of patients achieving $\geq 30\%$ decrease (score) in limitation of jaw function with the use of erenumab after 12 weeks of treatment compared to placebo.

There is a greater proportion of patients achieving $\geq 30\%$ decrease (score) in oral behaviors with the use of erenumab after 12 weeks of treatment compared to placebo.

There is a greater proportion of patients achieving $\geq 30\%$ increase in value in pressure pain thresholds in temporalis, masseter, trapezius muscles, TMJs and epicondyles with the use of erenumab after 12 weeks of treatment compared to placebo.

There is a greater proportion of patients achieving $\geq 30\%$ decrease in intensity and pain related disability (GCPS) with the use of erenumab after 12 weeks of treatment compared to placebo.

There is a greater proportion of patients achieving $\geq 30\%$ increase in score (impression of improvement/ impression of change/PGIC) with the use of erenumab after 12 weeks of treatment compared to placebo.

There is a greater proportion of patients achieving $\geq 30\%$ decrease (score) in anxiety and depression (change in HADS) with the use of erenumab after 12 Weeks of treatment compared to placebo.

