12.4 Final Analysis Plan

The main goal of the statistical analyses is to estimate change in study primary and secondary endpoints to evaluate efficacy of Erenumab. Intention to treat analysis will be performed using a within-subjects student's pair t-test or repeated measures ANOVA (if more than two time points) to determine significant reduction in pain after drug intervention in each patient. Subsequently, a between-subjects unpaired t-test or two-way mixed designed ANOVA (if more than two time points) will be performed to determine difference between the placebo and erenumab groups. *Post-hoc analysis* will only be conducted following a significant ANOVA test, to protect from Type I errors. We will use a 2-way between subject's repeated measure ANOVA design to determine difference between the Erenumab group and placebo group, or a between-subjects unpaired t-test if two groups only. We will also use student's paired t-test to determine time points of significance. 50% reduction in pain days will be determined as a function of baseline pain days. Where, appropriate similar statistical procedures will be used for secondary endpoints.

Descriptive statistics for safety measures will also be calculated.

We will collect the following data for descriptive purposes and, if necessary, to use as covariates: Demographic information (age and race/ethnicity), rescue medication history, psychological factors and perceived change in overall status (PGIC).

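### The primary endpoint is defined as different quantities, 12.4 does not name the deciding test, and the 28-day baseline conflicts with 5.4.1 and Appendix A

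*Combined protocol and SAP*

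**What the plan says.** Five places describe the primary endpoint or hypothesis.

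- Protocol summary: a change from baseline, "representing the mean of daily average pain intensity score values (0-100 scale) derived from Daily Symptom Diaries for 12 weeks". This is one mean over the whole treatment period.
- Section 3.2.1: a monthly mean change from baseline, computed "for each month/cycle (4 weeks/28 days) during the 12 weeks (3 cycles) of treatment and the last month prior last visit (Follow up". This gives four values.
- Section 4: the arms are compared "in the monthly pain intensity score (on a 0-100 scale) during the 12 week treatment period". No month is named.
- Section 12.1: "Erenumab produces greater change in average pain score (0-100 scale) from Visit 1 to Visit 4 than placebo". No averaging window is given.
- Section 12.3.2, which sits under the interim-analysis heading 12.3: "The primary endpoint is change from Visit 0 to Visit 4 in average pain level (0-100) calculated in the month prior to the visit".

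For the test, 12.4 says "a between-subjects unpaired t-test or two-way mixed designed ANOVA (if more than two time points) will be performed to determine difference between" the arms, and that post-hoc comparisons "will only be conducted following a significant ANOVA test, to protect from Type I errors".

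The baseline is 28 days after Visit 0 in section 4 and four weeks in the 7.2 heading. Section 12.1 also gives four weeks, for pain days: "change from baseline phase (4 weeks) through the 12 weeks treatment phase (3 cycles) until Visit 4". Against this, 5.4.1 places randomisation no later than 7 days after Visit 0, and Appendix A places Visit 0 one to three weeks before Visit 1. Footnote B to Appendix A works from an interval of about one week and has Visit 0 repeated otherwise.

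**The concern.** A 12-week mean, a set of monthly changes and a last-month change are different estimands. They coincide only if the arm difference is constant over time, and even then their precision differs. Without a statement of which one governs, the same data can support opposite conclusions about efficacy.

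Two further gaps add to this. Read literally, 12.3.2 has no baseline: the diary is first issued at Visit 0, so no diary month precedes that visit. And the baseline on which every version depends has two incompatible lengths in text that sites use to schedule visits.

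**Working it through.** **1. The windows side by side** (Visit 1 = Day 0, 28-day cycles, Visit 4 on Day 84)

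- Summary: days 0-83 as one mean.
- 3.2.1: days 0-27, 28-55, 56-83, and the follow-up month 84-111.
- Section 4: monthly score within days 0-83, month not named.
- 12.3.2: 84 - 28 = 56, so days 56-83 only.
- 12.1: ends at Visit 4 with no window, so it fits more than one of the above.

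Illustration with assumed arm differences in months 1, 2, 3:

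- 4, 8, 12 points: 12-week mean (4 + 8 + 12)/3 = 8; last month 12.
- 12, 10, 6 points: 12-week mean 28/3 = 9.3; last month 6.

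**2. Baseline length against the stated duration**

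- The plan's 21 weeks: 28 (baseline) + up to 7 (randomisation to Visit 1, section 7.2.1) + 112 (Visit 5) = 147 days = 21 × 7. Reproduced.
- Appendix A and footnote B: 7 + 112 = 119 days = 17 weeks, up to 21 + 112 = 133 days = 19 weeks. Sections 6.3 and 9.1 say 18 weeks.
- Diary compliance: 0.80 × 28 = 22.4, so 23 entries. Seven days is 7/28 = 25% and 21 days is 21/28 = 75%. On those timings nobody could reach 80% of a 28-day baseline before randomisation.

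**3. Precision of the two single-number endpoints** (assumed equal monthly variance σ² and common correlation ρ)

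- Var(month 3 - baseline) = 2σ²(1 - ρ).
- Var(12-week mean - baseline) = σ²[(1 + 2ρ)/3 + 1 - 2ρ] = (4/3)σ²(1 - ρ).
- Ratio = 2 ÷ (4/3) = 1.5 for any ρ.

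**4. How often the verdicts differ**

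Inputs: 60 less 15% dropout (12.2) = 51 completers, taken as 26 v 25. Assumptions, since the documents give no figures: ρ = 0.5, 0.7, 0.8; an effect that is constant or builds as 1/3, 2/3, 1; effect size in SDs of month-3 change; two-sided 5%; mixed ANOVA without sphericity correction; 40,000 simulated trials per scenario.

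- Month 3 v 12-week mean, 0.5 SD: opposite verdicts in about 23-24% (constant) and 21% (building). The individual tests have only about 30-57% power here.
- The same at 0.926 SD, which gives month 3 90% power (0.926 × √(26 × 25/51) = 3.31): 8-9% (constant) and 17-18% (building).
- Sensitivity, AR(1) correlation 0.8, 0.5 SD: 26% (constant) and 15% (building).
- Group main effect v group-by-time interaction, 0.5 SD, ANOVA on baseline plus months 1-3: opposite in about 43-48% (constant) and 34-39% (building). On the three change scores: about 57% and 36-37%.

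**5. Type I error**

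- Free choice between the month-3 and 12-week-mean t-tests: about 7.4-8.0%.
- With the 12.4 ANOVA gate on baseline plus months 1-3: 2.5-2.9% (5.1% under AR(1) 0.8, gate passed by either effect).
- With the gate on the three change scores, passed by either effect: 5.6-5.8% (6.4% under AR(1) 0.8).

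**The case against.** The strongest reply is that the document has a natural hierarchy. Section 3.2.1 is headed as the primary outcome measure and is the most detailed definition. Section 4 also uses the monthly score, the summary may be a loose précis of it, and 12.3.2 belongs to the interim-analysis section. With several months, 12.4 then points to the mixed ANOVA. Much of this stands, and it makes 3.2.1 the best candidate. It does not settle the matter: no sentence gives 3.2.1 precedence, and under it 12.4 still names neither the deciding effect nor the role of the follow-up month.

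It is also fair that the short intervals look like leftovers, since the contents list still shows one to three weeks for 7.2. But 5.4.1 and Appendix A are working instructions, and nothing marks them as void.

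Four stronger readings may tempt a reader and are not supported:

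- *The plan inflates type I error.* That needs a free choice by t-test. With the 12.4 gate on baseline plus months 1-3, error stays at about 5% or below; on change scores it is only slightly above.
- *A Day 90 Visit 4 pushes the last-month window outside the third cycle.* The Appendix A pages that give Day 90 also give Day 60 for Visit 3. Days 62-89 then lie within the third dosing interval. The two calendars disagree, but not with that result.
- *Section 12.1 confirms the last-month endpoint.* It states no window.
- *Participants were randomised on a short baseline.* Nothing in the documents shows this.

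**Conclusion.** The point holds. The summary, 3.2.1 and 12.3.2 define different primary quantities, 12.4 makes the test depend on the choice left open, and the 28-day baseline cannot coexist with 5.4.1, Appendix A and footnote B. The text inconsistencies are certain from the documents.

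The size of the effect rests on assumed correlations and effect shapes. On those, choosing between month 3 and the 12-week mean reverses the verdict in roughly one trial in five to one in four at 0.5 SD, and in 8-18% when month 3 has 90% power. The choice of ANOVA effect reverses it in about a third to over a half at 0.5 SD, depending on data layout and effect shape. Low power contributes to the 0.5 SD figures. The harm is mainly that the deciding result is not fixed in advance.

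One limit applies. The protocol's supplemental materials list a separate Statistical Analysis Plan, which was not available. It may rank the endpoints. The protocol would still contradict itself, and visit timing would still need to be reconciled.

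**What to change.** Before unblinding:

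- State one primary endpoint, with one baseline window and one outcome window, in identical words in the summary, 3.2.1, 4, 12.1 and 12.3.2. The sponsor chooses: for example the 28 diary days before Visit 4, or the 12-week mean. Make the other windows, including follow-up, secondary.
- Name in 12.4 the single between-group test of that endpoint. If it is an ANOVA, name the deciding effect and the time points that enter it.
- Reconcile 5.4.1, Appendix A (the one-to-three-week interval, and the Day 84/112 and Day 90/120 calendars) and footnote B with the baseline chosen. Say how any days between randomisation and Visit 1 count.
- If anyone was randomised on a shorter baseline, state how they are analysed.
- Align the separate SAP to the same words, and correct 18 v 21 weeks as housekeeping.

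The cost is a wording amendment with no new data collection. Any baseline diary days that were never collected cannot be recovered.

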12.4 Final Analysis Plan

The main goal of the statistical analyses is to estimate change in study primary and secondary endpoints to evaluate efficacy of Erenumab. Intention to treat analysis will be performed using a within-subjects student's pair t-test or repeated measures ANOVA (if more than two time points) to determine significant reduction in pain after drug intervention in each patient. Subsequently, a between-subjects unpaired t-test or two-way mixed designed ANOVA (if more than two time points) will be performed to determine difference between the placebo and erenumab groups. *Post-hoc analysis* will only be conducted following a significant ANOVA test, to protect from Type I errors. We will use a 2-way between subject's repeated measure ANOVA design to determine difference between the Erenumab group and placebo group, or a between-subjects unpaired t-test if two groups only. We will also use student's paired t-test to determine time points of significance. 50% reduction in pain days will be determined as a function of baseline pain days. Where, appropriate similar statistical procedures will be used for secondary endpoints.

Descriptive statistics for safety measures will also be calculated.

We will collect the following data for descriptive purposes and, if necessary, to use as covariates: Demographic information (age and race/ethnicity), rescue medication history, psychological factors and perceived change in overall status (PGIC).

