7.2.1 Randomization

Prior randomization, the participant to be eligible is required to have 80% compliance with the Daily Symptom Diary for the baseline period after visit 0 and reported an average pain level ≥ 30 on a numerical rating scale (0-100) or had experienced a pain level ≥ 30 on the same scale for at least 3 days the week before randomization. Participants then will be randomly assigned to one of two groups (Erenumab or placebo) and will be scheduled for Visit 1. Visit 1 should be scheduled within a week after randomization

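### Section 12.4 gives an uncontrolled before-after test an inferential role and does not say that only the comparison with placebo decides efficacy

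*Combined protocol and SAP*

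**What the plan says.** Section 12.4 opens by stating that the analyses are meant to "estimate change in study primary and secondary endpoints to evaluate efficacy of Erenumab". It then names the first procedure: "Intention to treat analysis will be performed using a within-subjects student's pair t-test or repeated measures ANOVA", the ANOVA being for more than two time points. The purpose given for this step is "to determine significant reduction in pain after drug intervention in each patient".

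The comparison of arms comes next: "Subsequently, a between-subjects unpaired t-test or two-way mixed designed ANOVA". It is named once more later in the section. The within-subject test also returns: "We will also use student's paired t-test to determine time points of significance". Similar procedures are to be applied to the secondary endpoints where appropriate.

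Elsewhere efficacy is comparative. The primary objective in section 3.1 is stated against placebo. Section 4 evaluates efficacy as the difference between the arms. The primary hypothesis in section 12.1 is that "Erenumab produces greater change in average pain score (0-100 scale) from Visit 1 to Visit 4 than placebo". Section 12.1 also carries a general hypothesis without a comparator: "Erenumab reduces pain and restores function in patients suffering of TMD".

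No section says which of the two kinds of test decides, or that the within-subject tests are only descriptive.

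**The concern.** A before-after test within the treated arm counts every source of improvement as change after the drug. The documents themselves point to several sources other than the drug:

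- Section 2.1 notes that TMD pain remits or improves over time in some patients.
- Sections 5.1 and 7.2.1 admit patients on recent pain of at least 30 (diary average, or at least 3 days in the preceding week), which invites regression to the mean.
- Section 6.6 allows over-the-counter rescue analgesics.
- Placebo response is the reason for having the control arm.

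Two faults need no assumption about size. A paired t-test concerns the mean change of a group, so it cannot establish a reduction in each patient. And the plan's only intention-to-treat label sits on a procedure that makes no randomised comparison.

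At stake is what a report could present as prespecified. With the text as it stands, a significant within-arm p-value could be quoted as a planned efficacy result beside a between-arm comparison that shows nothing.

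**Working it through.** **Plan's own figure.** The documents give no error rate for the within-subject test, so there is none to reproduce.

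**Inputs from the documents.** 30 patients per arm, alpha 0.05 and 15% dropout (section 12.2). 30 × 0.85 = 25.5, so I use n = 26 and n = 30. Sidedness is not stated; I take two-sided.

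**Assumed input.** The expected change on placebo, the SD of change and the within-patient correlation are not given. I therefore vary dz, the mean improvement divided by the SD of the change score, and set it equal in both arms (inert drug).

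**Within-arm test.** The paired t statistic has n − 1 degrees of freedom and noncentrality dz × √n. The chance of a significant reduction is P(T > t[0.975, n−1]). The critical values are 2.060 (n = 26) and 2.045 (n = 30). Example: dz = 0.5, n = 30 gives noncentrality 0.5 × √30 = 2.739 and probability 75%.

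| Common improvement dz | n = 26 | n = 30 |
|---|---|---|
| 0 | 2.5% | 2.5% |
| 0.2 | 16% | 18% |
| 0.3 | 31% | 36% |
| 0.5 | 69% | 75% |
| 0.8 | 97.5% | 98.8% |

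On the 0–100 scale with an assumed SD of change of 20, a 5-point fall is dz = 5/20 = 0.25 and gives 26% at n = 30. A 10-point fall is dz = 0.5 and gives 75%.

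**Between-arm test.** With equal improvement the expected difference in change is zero, so the unpaired t-test keeps its level. In 40,000 simulated trials per setting the rejection rate was 4.8–5.2% for dz from 0 to 0.8 at n = 26 or 30.

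**Regression to the mean alone.** Take a normal baseline with mean μ and SD σ, truncated at 30, and correlation ρ with follow-up. The expected fall is (1 − ρ) × σ × φ(a)/(1 − Φ(a)), with a = (30 − μ)/σ. For μ = 40, σ = 20, ρ = 0.6: a = −0.5, and the fall is 0.4 × 20 × 0.3521/0.6915 = 4.07 points. This is dz 0.24, and the two-sided paired test rejects in 25% of trials at n = 30. Over the assumed settings tried (μ 35–50, σ 15–20, ρ 0.6–0.9) the range is 6–32%, against 5% two-sided with no change.

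**Disagreement between the two tests.** At dz = 0.5 with an inert drug, a significant fall on erenumab beside a non-significant between-arm test occurs in about 66% (n = 26) to 73% (n = 30) of trials. With p the within-arm probability, significance on erenumab but not on placebo has probability p(1 − p). Its maximum is 25%, at p = 0.5, which is dz about 0.4.

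**Which patients.** The text does not say whether the paired test is run in the erenumab arm, in each arm or in everyone. Pooled over 60 patients at dz = 0.5 it would be significant in 97% of trials.

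**The case against.** The best defence is that the plan already treats efficacy as comparative. Sections 3.1 and 4 and the primary hypothesis in 12.1 all refer to placebo, and 12.4 names the between-arm test twice. The order of sentences in 12.4 is a sequence, not a hierarchy. The comparator-free hypothesis in 12.1 stands between a statement about differences from placebo and the comparative primary hypothesis. All of this stands.

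A reader might infer that the plan takes the within-arm result as the drug effect. The documents do not support that, because no sentence makes a significant within-arm test sufficient for efficacy. A reader might also infer that an inert drug would very often be declared effective. That is not established either. The common improvement is not given, and the rate is only 16–36% at 0.2–0.3 SD and 6–32% under the regression-to-the-mean settings. Nor is significance on erenumab alone a planned decision rule; the 25% describes a possible misreading.

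It is also fair to say that the paired test keeps its level against its own null of no change. The percentages in the table are its power to detect a common improvement. They become false-positive rates only when the result is attributed to the drug.

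The Supplemental Materials list a separately stored Statistical Analysis Plan, which might settle the matter but does not mend the wording of 12.4.

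What the defence does not meet is the text itself. The test is given an inferential purpose after drug intervention, in a section about efficacy, under the intention-to-treat label, and is reused for time points. Nothing excludes the uncontrolled reading.

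**Conclusion.** The point holds as a fault of wording and role. Section 12.4 assigns inference to an uncontrolled test, describes that test as showing something it cannot show, and leaves open which test decides.

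The size depends on an improvement that the documents do not state. For an assumed 0.2 to 0.8 SD in both arms and an inert drug, the chance of a significant reduction within the erenumab arm runs from about 16% to 99% (26–30 patients, two-sided 0.05). With no change at all it is 2.5% in that direction. The between-arm comparison stays at 5% throughout. These figures show what attributing the within-arm result to the drug would cost. They are not the error rate of a rule that the plan states.

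**What to change.** In section 12.4:

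1. State that efficacy is concluded only from the between-arm difference in change, with patients analysed in the arm to which they were randomised, and attach the intention-to-treat label to that comparison.
2. Report within-arm mean changes with confidence intervals as description only.
3. Delete the words that refer to each patient.
4. Take statements about individual time points from between-arm contrasts, not from paired t-tests.
5. Apply the same rule where these procedures are carried over to the secondary endpoints.

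Adding a comparison with placebo to the general hypothesis in 12.1 is optional, because the primary hypothesis there already has it.

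The cost is a wording amendment, with no extra patients, visits or data. It brings 12.4 into line with sections 3.1, 4 and 12.1.

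### Section 12.4 does not fix the primary between-arm test, allows adjustment for PGIC (a secondary outcome) and leaves baseline pain off the covariate list

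*Combined protocol and SAP*

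**What the plan says.** Section 4 makes efficacy a between-arm question: "Efficacy will be evaluated as the difference between Erenumab arm and the placebo arm in the monthly pain intensity score".

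Section 12.4 gives two rules for that comparison. The first switches on the number of time points: "a between-subjects unpaired t-test or two-way mixed designed ANOVA (if more than two time points) will be performed to determine difference". The second, later in the same paragraph, prescribes a two-way repeated-measures ANOVA, "or a between-subjects unpaired t-test if two groups only". Neither rule names the ANOVA term that decides efficacy.

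The number of time points depends on the section:

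- Section 3.2.1 scores pain at baseline, then "for each month/cycle (4 weeks/28 days) during the 12 weeks (3 cycles) of treatment and the last month prior last visit (Follow up".
- Section 12.3.2 uses two points: "The primary endpoint is change from Visit 0 to Visit 4 in average pain level (0-100) calculated in the month prior to the visit".
- Section 12.1 also uses two points, but from Visit 1 to Visit 4.
- The Protocol Summary and Section 4 speak of the 12-week treatment period.

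On covariates, Section 12.4 says "We will collect the following data for descriptive purposes and, if necessary, to use as covariates". The list is age, race/ethnicity, rescue medication history, "psychological factors and perceived change in overall status (PGIC"). Baseline pain is not on it.

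**The concern.** If the rule that selects the primary test can be read two ways, the test can be chosen after the data are seen, and the same data may give different verdicts.

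The covariate list raises two further questions. PGIC is a secondary outcome (Section 3.2.2) with its own efficacy hypothesis (Section 12.1). Appendix A schedules it at Visits 1 to 5, and Section 12.4 does not say which visit's value would be used. Any value recorded after the first injection can carry part of the drug effect, so adjusting for it removes part of what the trial is meant to detect. Baseline diary pain, by contrast, is required of every randomised participant (Section 7.2.1) and is usually a strong predictor of later pain, yet it is not listed.

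**Working it through.** **The plan's own figure.** Section 12.2 states 60 patients, 90% power, alpha 0.05, effect size 0.5 and 15% dropout. A two-sided unpaired t-test at 0.5 SD needs 86 per arm, so 172 in total, or 172/0.85, rounded up to 203, with dropout. The stated 60 is not reproduced. That is a separate matter; here it only sets the evaluable number: 60 × 0.85 = 51, taken as 26 v 25.

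**Which test each rule selects.** The trial has two arms (Section 5.4).

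| Endpoint wording | Time points | First rule | Second rule, read literally |
|---|---|---|---|
| Section 3.2.1, with follow-up month | 5 | mixed ANOVA | t-test |
| Section 3.2.1, to Visit 4 only | 4 | mixed ANOVA | t-test |
| Section 12.3.2, Visit 0 to 4 | 2 | t-test | t-test |
| Section 12.1, Visit 1 to 4 | 2 | t-test | t-test |

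With two groups and two time points the group-by-time F equals the square of the t statistic on change, so disagreement is 0%. The conflict arises only under Section 3.2.1.

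**How often the tests disagree under Section 3.2.1.** Simulation used 40,000 trials per case, 26 v 25, equal correlations and complete data, comparing the t-test on change (baseline to month 3) with the group-by-time F at 0.05. The effect is 0.5 raw-score SD at month 3. Correlations of 0.5 and 0.7 are assumed.

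| Case | Disagreement at 0.5 / 0.7 |
|---|---|
| 4 points, constant effect | 21.6% / 21.2% |
| 4 points, gradual effect | 19.6% / 20.6% |
| 5 points, constant effect kept at follow-up | 24.5% / 23.4% |
| 5 points, constant effect lost at follow-up | 30.3% / 28.1% |

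With no effect and four points, each test alone rejects in about 5% of trials and at least one rejects in 8.2% / 8.5%. Disagreement is twice the either-test rate minus the two single rates: 2 × 8.2 − 5.0 − 5.0 = 6.4% at correlation 0.5.

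**PGIC as covariate.** Assume PGIC depends on arm only through pain change and correlates r with that change within arm. Then the adjusted effect = true effect × (1 − r²). For a true 10 points:

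- r = 0.5: 10 × 0.75 = 7.5
- r = 0.7: 10 × 0.51 = 5.1

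Both values of r are assumed.

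**Baseline diary pain as covariate.** The effect is 0.5 raw-score SD, and ρ is the assumed correlation between baseline and month-3 means. The change score has SD √(2(1 − ρ)); single-time-point ANCOVA has residual SD √(1 − ρ²). The noncentrality is (0.5/SD) × √(26 × 25/51) = (0.5/SD) × 3.570, two-sided 0.05, with 49 df for change and 48 for ANCOVA.

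| ρ | Change: SD, noncentrality, power | ANCOVA: SD, noncentrality, power |
|---|---|---|
| 0.5 | 1.000, 1.785, 41.7% | 0.866, 2.061, 52.4% |
| 0.6 | 0.894, 1.996, 49.9% | 0.800, 2.231, 59.0% |
| 0.7 | 0.775, 2.304, 61.8% | 0.714, 2.500, 68.8% |

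Section 12.2 does not say which SD its 0.5 refers to. If it means change-score SDs, the change-score power is 41.7% throughout and ANCOVA gives 52.4%, 49.8% and 47.5%.

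**The case against.** The strongest reply is that Sections 12.1 and 12.3.2, both in the statistical chapter, describe a two-point change. Both rules then select the t-test and nothing is left to choose. The second rule may also be a slip for a repeat of the first, since read literally it means the ANOVA in its own sentence could never be used in a two-arm trial. Both remarks are fair. They make the conflict conditional, but settling it means preferring those sections to Section 3.2.1, which is the section that defines the primary outcome, and Section 12.4 does not say to do so.

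The disagreement rates rest on assumed correlations, on choosing the group-by-time term, and on complete data. Two valid tests of different hypotheses at moderate power will often disagree, and that is not bias. When the effect is lost at follow-up, the F-test is partly detecting that loss. All of this stands; the rates show only that the choice matters.

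PGIC adjustment is optional, and the Visit 1 value precedes the first injection. However, neither the trigger nor the visit is stated. Baseline pain already enters through the change score or as a time level in the ANOVA, so its absence from the list is not an error.

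Supplemental Materials lists a separate Statistical Analysis Plan that was not available for this review and may settle all of this.

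**Conclusion.** The point holds in conditional form. Section 12.4 leaves the primary between-arm test open: there is no disagreement on the two-point endpoint, and about 20 to 30% on the Section 3.2.1 endpoint with a 0.5 SD effect (about 6% with none). Allowing post-injection PGIC as a covariate is a defect whatever the exact attenuation. Adding baseline diary pain is an improvement rather than a correction, worth about 7 to 11 percentage points of power when the effect is 0.5 raw-score SD. It does not restore 90%.

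A reader might infer three stronger things that the documents do not support:

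- That type I error is 8%. This would be so only if either test could count as primary, which the plan does not say.
- That the unadjusted change score is invalid. It is valid, only less precise.
- That the primary result will be adjusted for PGIC. The plan permits this without committing to it.

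Section 12.4 labels its analysis intention to treat ("Intention to treat analysis will be performed using a within-subjects student's pair t-test or repeated measures ANOVA"). Whether that label can be met is a different question. It turns on the 80% diary rule (Section 3.2.1) and on discontinuation from the study, including for worsening TMD (Sections 5.5.2, 6.3 and 9.1). Those passages, and the conflicting baseline period (Sections 4, 5.4.1 and 7.2, and Appendix A), need their own reconciliation. The size of any resulting bias cannot be estimated from the documents.

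**What to change.** 1. Reconcile the endpoint wording in the Protocol Summary and Sections 3.2.1, 4, 12.1 and 12.3.2. Then replace both test-selection rules with one named between-arm test and term. One suitable choice is the arm difference in the month before Visit 4, adjusted for baseline diary mean, two-sided 0.05. It can come from an ANCOVA or from a repeated-measures model of months 1 to 3 with that contrast. Label the within-arm and paired tests descriptive.
2. Remove PGIC from the covariate list, together with any other measure taken after the first injection. Rescue medication and psychological factors need the same timing check.
3. Add the baseline diary mean as a prespecified covariate.

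If the separate Statistical Analysis Plan already settles these points, Section 12.4 should refer to it.

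The cost is a small protocol amendment, which needs IRB approval under Section 15.2, with no extra patients, visits or measurements. The change should be made before unblinding. It does not address bias from scores that are missing for outcome-related reasons.
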